### **12.5.5. 12-Lead Electrocardiogram (ECG)**

12-Lead ECGs will be performed after the subject has been resting in a recumbent/supine position for at least 5 minutes. The ECG variables will include ventricular heart rate and the PR, QRS, QT and QTcF intervals. The ECGs will be signed and dated by a medically-qualified individual to confirm review of the ECG and verify whether any abnormalities are clinically significant. In general, abnormal, clinically significant ECGs are expected to be associated with an item recorded in medical history or with an AE. ECGs will be assessed at Screening and at T24h ( $\pm$  2 hour). Clinically significant changes in ECG (i.e., QTcF should be <450 msec / < 470

msec for female / male subjects, respectively; and an increase of QTcF of > 30 msec will be considered an AE.

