	
neurologic AE since this could occur because of tissue trauma and inflammation from the surgery.
 
 
○ Sensory deficits or clinically significant persistent sensory change beyond the area proximal to the incision at time of discharge, such as allodynia or hyperalgesia, must be designated as a neurologic AE. Subjects will be followed until there is full return to baseline for the neurosensory assessment or until there is a determination that it has reached a resolution or establishment of a new baseline.
 
● ECGs, standard clinical labs at screening and T96h post-treatment [except as noted for pregnancy test]. The Investigator is responsible for determining if out of range laboratory values are clinically significant or not. All clinically significant values will be recorded in the eCRF and followed until resolution.             
 
○ ECG at screening and T24h ±2 hr
 
○ Hematology at screening and T96h: hemoglobin, hematocrit, white blood cell count with differential, red blood cell count, platelet count,
 
○ Blood Chemistry at screening and T96h: Alanine aminotransferase (ALT; SGPT) and Aspartate aminotransferase (AST; SGOT), total bilirubin (TBili), gamma-glutamyl transferase (GGT), blood urea nitrogen (BUN), creatinine, alkaline phosphatase (ALK), lactate dehydrogenase (LDH), sodium, potassium, calcium, chloride and glucose.
 
○ Serum and urine pregnancy test for FCBP: βhCG test at screening and urine test usually to be done within 24 hours prior to surgery.
 
○ Urinalysis at screening and T96h: including macroscopic analysis and, if indicated, microscopic analysis.
 
 
 

Primary Endpoint:
	
Weighted sum of pain intensity (SPI) assessments = Area Under the Curve (AUC) of the NRS current pain intensity scores from T0 to 96h at rest (<math>AUC_{0\text{ to }96h}</math>).

Key Secondary Endpoints:
	
The key secondary endpoints are:
 
 
● Percentage of subjects who do not require opioids or are opioid free (OF) from T0 to T96: <math>OF_{0\text{ to }96h}</math>
 
● Total opioid consumption (in daily oral morphine equivalents) = OC from T0 to T96h: <math>OC_{0\text{ to }96h}</math>
 
● Using NRS at rest: <math>AUC_{0\text{ to }W1}</math>
 

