Safety Endpoints:	
The following safety endpoints will be evaluated:
 
 
• Incidence of TEAEs or treatment-emergent SAEs from D0/T0 through D29: Note that all AEs will be recorded from the time the informed consent form (ICF) is signed through D29 (or D36 as applicable). TEAEs are defined as AEs occurring post T0 (end of study treatment infiltration).
 
• Surgical site assessment / wound evaluations to assess for atypical skin reactions, e.g., erythema, pain, pruritus, bruising, swelling, bruising or other skin changes, should be evaluated and graded for severity and followed regularly until resolution or a stable baseline is achieved.
 
• Physical examination (PE) of the lower extremities and vital signs, including neurosensory testing of both lower extremities 
 
○ Note that any observed or reported sensory deficit or clinically significant persistent sensory change remote from the immediate surgical site, such as allodynia or hyperalgesia, must be designated as a neurologic AE. Subjects should be followed until resolution or a stable baseline is achieved.
 
○ Numbness proximal to the incision need not be considered a neurologic AE since this could occur because of tissue trauma and inflammation from the surgery.
 
 
 
• ECG changes from screening to T24h post-treatment
 
• Clinically significant clinical labs changes from screening
 

Pharmacokinetics:	
Approximately 1/3rd of enrolled subjects at each site will participate in the PK study (48 in total; 12 in each treatment group). The PK population will include all subjects who have sufficient concentration-time profiles for estimation of PK parameters.
 
Based upon the PK results from the Phase 1 bunionectomy ascending dose safety study, the time points for whole blood collection will be at baseline (within the 30 min before the start of study treatment dosing), and T5min, T10 min, T15min,

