3. Vital signs: 1, 2, 4, 6, 12, 24 and every 8 hours thereafter (if awake at time of assessment between the hours of 00:00 and 06:00) until discharge from the inpatient unit (may not miss two consecutive assessments). There will be a ±5-minute window allowed for the collection of vital signs in the first 4 hours after the end of surgery, after which will be a ±15-minute window allowed.
4. A complete medical history and physical examination including all major body systems will be performed at Screening. In addition, at the following times, an interim medical history and targeted physical examination will be performed prior to surgery (if not done on D-1), and to capture changes after Surgery, at 96 hours (within 4 hours of discharge), and Day 8, Day 15 and Day 29 after the administration of study medication or if the subject terminates early, at that time if allowed. Body weight (kg), in indoor clothing, but without shoes, will be measured at Screening, at 96 hours and Day 29, or at the time of discontinuation. Height (in cm) will be measured and BMI will be calculated at Screening only.
5. Post-Surgery ECG should be performed at 24 hours (±2 hours) after study medication administration
6. Surgical Site assessment: 96 hours (±4 hours) after study medication administration but prior to discharge from the inpatient unit
7. Neurosensory Exam of the Foot / Great toe (bilateral): 96 hours after study medication administration but within 4 hours of discharge from the inpatient unit
8. Clinical Laboratory tests (chemistry, hematology, and urinalysis) should be performed at screening (note if not done during screening, then perform prior to surgery) and prior to discharge from the inpatient unit (Lab collection window for 96h is ±30 min)

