### 7.1.1. CA-008 Product Introduction

The active moiety of CA-008, capsaicin, has certain attractive properties for treatment of post-operative pain from a pharmaceutical perspective. CA-008 is water soluble and easy to inject through a 25 g needle or larger. It readily penetrates surgical site tissues where it releases capsaicin through a non-enzymatic pH-driven process. Local administration of CA-008 at or near the source of pain either topically, by infiltration or by instillation into a surgical site results in low systemic levels of capsaicin.

Capsaicin, however, is virtually insoluble in aqueous media or local anesthetic solutions which means that capsaicin formulations tend to be quite hydrophobic making them hard to inject and less likely to permeate surgical site tissues resulting in poor target engagement. Anesiva, which had been developing capsaicin for the management of post-surgical pain and osteoarthritis, solubilized capsaicin in polyethylene glycol (Hartrick 2011). The product was instilled into the open surgical site and after waiting for 5 minutes, was removed via surgical suction. This route of administration was inconvenient and limited exposure of capsaicin only to the exposed surfaces of cut tissue and bone.

CA-008 was created to improve delivery of capsaicin without having to account for its poor solubility profile in tissues. CA-008 provides an aqueous formulation that could be simply infiltrated in the wound site to achieve local capsaicin release to produce a maximal effect. The free base form of CA-008 rapidly breaks down at physiological pH to yield capsaicin and a cyclic urea, as shown in the scheme below:

CA-008 was specifically selected for development due to its short half-life (<5 min) at neutral pH. In Tris buffer at pH 7.4 and 37°C, it completely breaks apart to capsaicin and CA-101 as the sole degradants.

The cyclic urea (CA-101) formed has not been previously evaluated for biological activity and it was shown to be inactive. While not a known compound in the clinical literature, its safety was evaluated in all nonclinical studies with CA-008. The toxicokinetic profiles for CA-008, CA-101, and capsaicin were determined in GLP safety studies and in a Phase 1 ascending dose safety study in patients undergoing bunionectomy.

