### 7.1.3. Capsaicin PK

Other than by ingestion, most human exposure to capsaicin is from topical administration therapeutically with ointments or patches as noted above or for self-defense or noxious effects with pepper spray. Topical capsaicin in humans is rapidly absorbed through the skin (Hayman 2008). Additionally, capsaicin is often used in basic science studies, such as in experimental pain studies (animal and human), where the main administration method is intradermal or intraplantar injections.

Systemic PK data for topical capsaicin is somewhat limited. In 173 patients with PHN, painful human immunodeficiency virus-associated neuropathy and painful diabetic neuropathy, the highest  $C_{max}$  observed in any patient was 17.8 ng/mL (Babbar 2009). Sparse sampling resulted in most patients not having quantifiable levels. Plasma concentrations were fitted adequately using a 1-compartment model with first-order absorption and linear elimination. Capsaicin levels

declined very rapidly, with a mean population elimination half-life of 1.64 hours. Mean area under the curve and  $C_{\max}$  values after a 60-minute application were 7.42 ng\*h/mL and 1.86 ng/mL, respectively. Ninety-minute applications of Qutenza resulted in AUC and  $C_{\max}$  values approximated 1.78- and 2.15-fold higher than those observed after a 60-minute application. Due to capsaicin's TRPV1 mechanism of action of inducing a prolonged functional depolarization, the duration of pain relief extends well beyond the relatively limited time of its exposure to the target peripheral site.

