#### **15.7.3. Vital Signs and ECG**

Descriptive summaries (mean, SD, median, minimum, and maximum) of actual values and changes from Baseline will be calculated for vital signs and ECG. Detailed description of the analysis will be included in the Study SAP.

The incidence of abnormal ECG findings will be summarized.

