8.7 ECG Examination

ECG examination will be assessed at screening and 24 hours (± 2 hours) after study medication administration.

Number of subjects with abnormal results will also be summarized by treatment and time point. All ECG data will be listed.

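### The SAP plans no table of ECG intervals or their change from screening, although the protocol plans that summary and names ECG change as a safety endpoint

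*Protocol*

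**What the plan says.** **Collection.** Protocol 12.5.5 collects ventricular rate, PR, QRS, QT and QTcF, and says "ECGs will be assessed at Screening and at T24h", with a 2-hour window either side of T24h. Table 1, footnote 5, agrees: "Post-Surgery ECG should be performed at 24 hours (±2 hours) after study medication administration". Protocol 9.1.4 and SAP 8.7 give the same time. No other post-dose ECG is scheduled.

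**Endpoint and trigger.** The synopsis lists "ECG changes from screening to T24h post-treatment" among the safety endpoints. Protocol 12.5.5 makes a QTcF rise above 30 msec an adverse event and sets QTcF limits.

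**Protocol analysis.** Section 15.7.3 plans mean, SD, median, minimum and maximum: "actual values and changes from Baseline will be calculated for vital signs and ECG". It separately plans the incidence of abnormal ECG findings and leaves the detail to the SAP.

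**SAP analysis.** Section 8.7 says "Number of subjects with abnormal results will also be summarized by treatment and time point" and that all ECG data will be listed. The only ECG table in the SAP's list is 14.3.7, on abnormal findings. Section 12, on changes from the protocol's analyses, declares none.

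**Timing wording in the synopsis.** Under safety assessment times, a lead-in reads "ECGs, standard clinical labs at screening and T96h post-treatment", while the sub-bullet beneath it puts the ECG at screening and T24h.

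**The concern.** The protocol plans two ECG summaries: continuous values with their changes, and the incidence of abnormal findings. The SAP carries only the second into its ECG section and table list. The one omitted is the one that matches the synopsis endpoint, which is a change.

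A count of abnormal tracings is a coarse measure, and SAP 8.7 does not define abnormal. A modest average lengthening of QTcF in one arm could leave most subjects below the 30 msec trigger and within the limits. It would then show in neither the abnormal counts nor the adverse-event tables, only in a subject listing that nobody is asked to summarise. Phase 1 treated 6 subjects at 4.2 mg (Protocol Table 2) and this trial plans about 36, so the ECG data here deserve the summary the protocol promised.

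A second matter is how a clean result would be read. With one post-dose tracing at T24h, the result describes that time and not the first hours after dosing.

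**Working it through.** **1. Protocol against SAP.** The documents give no precision or sample size for ECG, so there is no plan figure to reproduce. Set side by side:

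| Safety measure | Protocol plan | SAP text | SAP table |
|---|---|---|---|
| Vital signs | values and changes (15.7.3) | values and changes (8.5) | 14.3.4, includes change |
| Laboratory tests | values and changes, shifts (15.7.2) | values and changes, shifts (8.8) | 14.3.2.x, includes change |
| ECG | values and changes, plus abnormal incidence (15.7.3) | abnormal counts and a listing (8.7) | 14.3.7, abnormal only |

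ECG is the only one of the three that loses its change summary. The only scheduled pre-dose ECG is at screening, so change from baseline here means change from screening, as in the synopsis endpoint.

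**2. What the missing table could show.** The 95% half-width for a difference in mean change between two arms of 36 is 1.96 × SD × √(2/36) = 0.462 × SD. The SD of QTcF change is not in the documents, so I assume 8 to 20 msec:
- SD 8: 0.462 × 8 = 3.7 msec
- SD 20: 0.462 × 20 = 9.2 msec

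Both are well below 30 msec.

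**3. What the 30 msec trigger would show instead.** Suppose an arm's mean QTcF change is 10 msec, placebo's is 0, and changes are normal (illustrative assumptions). The expected number per 36 with a rise above 30 msec is 36 × P(Z > (30 − mean)/SD):

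| SD | Shifted arm | Placebo |
|---|---|---|
| 8 | 36 × P(Z > 2.5) = 36 × 0.0062 = 0.2 | 36 × P(Z > 3.75) < 0.01 |
| 10 | 36 × P(Z > 2) = 36 × 0.0228 = 0.8 | 36 × P(Z > 3) = 36 × 0.0013 = 0.05 |
| 20 | 36 × P(Z > 1) = 36 × 0.159 = 5.7 | 36 × P(Z > 1.5) = 36 × 0.067 = 2.4 |

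At the smaller SDs, fewer than one subject in the arm would be expected to trip the trigger.

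**4. Position of T24h relative to exposure.** Protocol 7.1.3 describes capsaicin after a dermal patch "with a mean population elimination half-life of 1.64 hours". Number of half-lives = t / 1.64, and fraction remaining = 2 to the power of minus that number:
- 22 h: 13.4 half-lives, 0.009%
- 24 h: 14.6 half-lives, 0.004%
- 26 h: 15.9 half-lives, 0.002%

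The other figures in the protocol are shorter. The oral capsaicin half-life of 24.9 min (7.1.2) gives 1440/24.9 = 57.8 half-lives. The prodrug was chosen "due to its short half-life (<5 min) at neutral pH" (7.1.1).

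None of these is a half-life of capsaicin after CA-008 infiltration, and none is given for CA-101. If slow release from the wound stretched the apparent half-life (assumed range), 4 h would leave 2^-6 = 1.6% at T24h and 6 h would leave 2^-4 = 6.3%. To leave 10% it would have to be 24 × ln 2 / ln 10 = 7.2 h.

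**5. Pairing with PK.** Of 16 post-dose PK samples, 11 fall at or before T4h (5, 10, 15, 30 and 45 min; 1, 1.5, 2, 2.5, 3 and 4 h). None of these has an ECG alongside. Only the T24h sample does.

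**The case against.** The best defence is that the SAP does not remove the analysis. Section 3 says continuous assessments will be summarised by treatment and time point with changes from baseline, and the word also in SAP 8.7 suggests an addition to other summaries. All ECG data are listed, a QTcF rise above 30 msec reaches the adverse-event tables, and safety is descriptive only. On this view all that is missing is a table shell.

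Part of this stands. A reader might infer that the SAP deliberately discards the interval data, and the documents do not support that: the data are collected and listed, and section 3 could nominally cover them. But section 3 also says specific sections take precedence, section 8.7 names no continuous summary, and no ECG table implements the general rule, while vital signs and laboratory tests have both text and tables. Listings and adverse-event counts do not replace a by-arm summary of smaller shifts.

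On timing, a reader might infer that the ECG endpoint cannot show any exposure-related effect. That goes too far. The 1.64 h value belongs to a patch, PK sampling itself runs to T24h, and a delayed or persistent effect, or a dose-group difference at T24h, could still appear. The T24h tracing does measure the synopsis endpoint as written. Nor do the documents make the case for moving the tracing. The Phase 1 time of peak concentration is not shown, and an earlier tracing would fall close to sedation, bupivacaine and possible oxycodone, while the later observation would be lost.

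**Conclusion.** The point holds as an undeclared gap between protocol and SAP. A summary planned in Protocol 15.7.3, matching a named safety endpoint, has no counterpart in SAP 8.7 or the table list. This conclusion needs no pharmacokinetic assumption. Its size depends on the SD of QTcF change: for an assumed 8 to 20 msec, the omitted table would resolve a difference in means to within 3.7 to 9.2 msec, while the planned outputs act mainly at the 30 msec trigger, the 12.5.5 limits or an undefined abnormal reading. The efficacy conclusions are unaffected.

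The timing of the ECG is a limitation to state, not a design error shown by the documents. T24h is about 15 half-lives after dosing if the patch value carries over, which is an extrapolation. The supportable statement is that the result does not assess effects near peak exposure.

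The T96h lead-in and T24h sub-bullet in the synopsis are an internal contradiction that must be reconciled.

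**What to change.** 1. In SAP 8.7 and the table list, add one safety-population table by arm. It should give heart rate, PR, QRS, QT and QTcF at screening and T24h with change from screening, using the statistics in Protocol 15.7.3. It should also give the number and percentage of subjects with a QTcF rise above 30 msec or a value outside the Protocol 12.5.5 limits. If the sponsor prefers to leave the summary out, declare and justify that in SAP section 12.
2. State in the SAP and the study report that the only scheduled post-dose ECG is at T24h (±2 h) and does not assess effects near peak exposure. If the half-life figure is cited, label it as patch-derived.
3. Reconcile the synopsis lead-in and sub-bullet on ECG timing with each other and with Table 1, Protocol 9.1.4 and 12.5.5, and SAP 8.7.

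The cost is one table, two or three sentences and an editorial correction. No ECG is added or moved, and the table uses data already collected.

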#### **12.5.6. Physical Examination**

A complete physical examination (PE) including all major body systems (HEENT, neurologic, cardiovascular, respiratory, gastrointestinal, dermatologic and musculoskeletal systems) will be performed at Screening, and interim PEs prior to Surgery, and additional interim PEs focused on the surgical site and neurosensory testing of both lower extremities at T96h prior to discharge from the inpatient unit, D8, D15 and D29/ET.

Body weight (kg), in indoor clothing, but without shoes, will be measured at Screening, at T96h prior to discharge from the inpatient unit and ET. Height in centimeters (cm) will be measured, and BMI will be calculated at Screening only. BMI shall be calculated as  $\text{kg/m}^2$ . Use the NIH website BMI calculator [http://www.nhlbi.nih.gov/health/educational/lose\\_wt/BMI/bmi-m.htm](http://www.nhlbi.nih.gov/health/educational/lose_wt/BMI/bmi-m.htm).

#### **12.5.7. Surgical Site Assessment**

The surgical site should be assessed to determine if any related AEs have occurred. Assessments will be conducted at T96h prior to discharge from the inpatient unit, and on the D8, D15 and D29/ET visits.

At T96h prior to discharge, the investigator will evaluate their satisfaction with the healing of the wound during this Surgical Site assessment using an 11-point scale (0-10) where a score of 0 is “Completely unsatisfied,” and a score of 10 is “Completely satisfied.” [Appendix 1E](#)

Assessments will also be performed at each of the Follow-up visits on Days 8, 15 and 29, or at the time of discontinuation. When assessed on Day 29, if the Investigator observes insufficient wound healing, the subject will be scheduled for a follow-up visit on Day 36. [Appendix 1F](#)

If there are atypical skin reactions, for example, erythema, pain, pruritus, bruising, swelling, bruising or other skin changes, they will be evaluated and graded for severity.

#### **12.5.8. Neurosensory Exam**

A neurosensory exam of the lower extremity (foot/great toe surgical site with contralateral comparison) will be conducted at screening, at T96h prior to discharge from the inpatient unit, on the D8, D15 and D29/ET (and D36 if necessary) visits. The exam will involve the dorsal aspect of the foot proximal to the great toe.

This evaluation will include the following (details described in [Appendix 1G](#)):

- Visual exam of the foot
- Deep Tendon Reflexes (normal, reduced or absent)
- Vibratory sensation (normal, reduced or absent)

- Monofilament Sensation (normal, reduced or absent)
- Allodynia to brush (pain (allodynia), hyperesthesia, normal, reduced or absent)

A persistent atypical sensory change after EOS, such as allodynia or hyperalgesia proximal to the surgical site will be reported as an AE. Numbness at or near the incision need not be considered an AE since this could occur due to tissue trauma and inflammation from surgery.

### 12.5.9. Assessment of Adverse Events

All SAEs will be documented and followed from the time the subject has signed the ICF until D29 or, if necessary, D36 after the completion of surgery. All SAEs and non-serious AEs will be documented and followed from the time of administration of study treatment until D29 or, if necessary, D36 after the completion of surgery. AEs that occur between Screening and the study procedure should be considered medical history and added to the subject's medical record. AEs that have been designated as possibly or probably related to study treatment will be followed until resolution or stabilization. Further details on AEs, including definitions, elicitation, and reporting are provided in [Section 13](#).

## 12.6. Efficacy, Safety and PK Endpoints

### 12.6.1. Efficacy Endpoints

Using NRS scores (at rest and with ambulation) a variety of time-specific summed pain intensity assessments (area under the curve or AUC for pain intensity) will be calculated comparing each CA-008 dosing groups to placebo.

